5.3 Dose Limiting Toxicity (DLT)

Toxicity will be assessed according to the NCI Common Terminology Criteria for Adverse Events Version 4.0 (CTCAE v4.0).

The Dose Limiting Toxicity Period will be the first 14 days from the start of the CED procedure.

Dose limiting toxicity (DLT) will be defined as:

- Any intolerable (as deemed by the patient or investigator) grade 2 or any grade 3 or higher neurological toxicity felt to be attributable to the CED infusion procedure or to the MTX110 injection with gadoteridol within a period of 14 days after the infusion.
- Any systemic treatment related grade 3 or higher hematologic or non-hematologic toxicity (after maximal medical management of nausea/vomiting/diarrhea) within a period of 14 days after the infusion.

If multiple toxicities are seen, the presence of a dose limiting toxicity should be based on the most severe toxicity experienced.

Dose modifications are described in Section 5.5.

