10.3 Sample Size and Accrual

The number of subjects enrolled in the safety study will depend upon the DLTs observed and the number of dose levels tested as the study progresses in accordance with an ATD followed by a 3+3 design. The ATD is expected to enroll 1 to 7 subjects with a minimum of 5 subjects in the 3+3 design. Additional subjects may be enrolled depending on the dose de-escalations, expansion of dose exploration, or exploration of intermediate doses that occur. Once these dose levels have been assessed, a detailed review of the safety and efficacy data will be performed and discussed with the FDA and the DSMC to discuss either further dose escalation or enrollment into the efficacy study.

Secondary Objective: The most recent Children’s Oncology Group study that treated children newly diagnosed with DIPG with a combination of radiation therapy and temozolomide resulted in an OS12 rate of 40% (SD ± 6.5%). A sample size of 19 patients achieves 80% power to detect a difference of 30% using a one sided exact binominal test. The target significance level is 5% and the actual significance level is 3.5% with this test. If 12 or more patients are alive at 12 months, the null hypothesis that OS12 is 40% will be rejected.

Stopping Rules:

Both the ATD and 3+3 have inherent stopping rules; however, it should be noted that this study will be stopped for further review by the DSMC and study team as well as FDA by:

- The occurrence of 1 or more irreversible neurological deficits that are grade 3 or higher and definitely related to the procedure based on evidence on MRI such as intraparenchymal hemorrhage, worsening edema or necrosis.

- If more than 20% of subjects develop significant, irreversible deterioration during the infusion.
- If more than 20% of subjects do not get study drug infused due to surgical complications during the catheter placement.

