In addition, all adverse reactions considered “serious” (also called Serious Adverse Events, or SAEs), regardless of relationship, must be entered in OnCore® and reported to the PNOC Operations Office within **1 business day**. SAEs will be reviewed and monitored by the UCSF DSMC on an ongoing basis, and will be discussed at the UCSF DSMC meeting, which take place every six (6) weeks.

If a death occurs during the treatment phase of the study, or within 30 days after the last administration of the study drug(s), and is determined to be related either to the investigational drug or to any research related procedure, the Study Chair and the PNOC Operations Office must be notified by the member institution within **1 business day**. The Study Chair or the PNOC Operations Office must then notify the UCSF DSMC Chair, or qualified alternate, within 1 business day of this notification. The contact may be by phone or e-mail.

Increase in adverse event rates

If an increase in the frequency of Grade 3, 4, or 5 Adverse Events (above the rate reported in the Investigator Brochure or package insert), the Study Chair or the PNOC Operations Office is responsible for notifying the UCSF DSMC at the time the increased rate is identified.

If at any time the Study Chair or the PNOG Operations Office halts enrollment or ends the study due to safety issues, the UCSF DSMC Chair and Manager must be notified within **1 business day** via e-mail. The UCSF DSMC must receive a formal letter within **10 business days**, and the UCSF IRB must be notified.

UCSF data and safety monitoring committee contacts:

UCSF DSMC Chair

[REDACTED]

[name]

[name]

UCSF DSMC Manager

[REDACTED]

[name]

[name]

UCSF DSMC Monitors

[name]

[name]

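### In the expansion, section 10.3 forces no stop for an irreversible grade 3+ neurological deficit that begins after the infusion, unless it is definitely procedure-related with MRI evidence

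*Combined protocol and SAP*

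**What the plan says.** Section 10.3 (Stopping Rules) first notes that "Both the ATD and 3+3 have inherent stopping rules". It then lists three events on which "this study will be stopped for further review by the DSMC and study team as well as FDA":

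1. One or more "irreversible neurological deficits that are grade 3 or higher and definitely related to the procedure based on evidence on MRI". No time window is given.
2. "If more than 20% of subjects develop significant, irreversible deterioration during the infusion". No attribution is required, and neither the denominator nor the times of assessment are stated.
3. "If more than 20% of subjects do not get study drug infused due to surgical complications during the catheter placement". This concerns failed delivery, not toxicity after dosing.

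Section 5.3 defines a neurological DLT more widely. Any grade 3 or higher event (or an intolerable grade 2 event) counts if it is felt to be "attributable to the CED infusion procedure or to the MTX110 injection with gadoteridol within a period of 14 days after the infusion". Section 6 applies the 14-day period after each CED procedure.

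Sections 5.5 and 10.2 use DLTs to run the accelerated titration design (ATD), the 3+3 stage and dose changes within a subject. No study-level rule based on DLTs is written for the 19-subject expansion.

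Appendix E requires the DSMC to be told of an increase in grade 3 to 5 events "above the rate reported in the Investigator Brochure or package insert". It gives no numeric margin.

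**The concern.** The primary objective (section 1.1) is the safety of repeated administration of MTX110, and the expansion is planned as the largest group at the recommended dose. The animal CED toxicity studies in Table 9 are all single-dose, so delayed or cumulative neurotoxicity of the drug is one of the main unknowns. The mandatory triggers are narrowest at that point. An irreversible grade 3 deficit that appears on day 3 and is ascribed to MTX110 is a DLT under 5.3 but meets no trigger in 10.3. The same holds if it is ascribed only probably to the procedure. During escalation the ATD and 3+3 rules give some cover. In the expansion nothing written takes their place, so whether to pause would rest on judgement, case by case.

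**Working it through.** **Step 1: what the section calculates.** The only design calculation in 10.3 is the 12-month survival test: n = 19, reject if 12 or more are alive, null rate 40%, alternative 70%. The exact binomial gives P(X ≥ 12 | 0.40) = 0.0352 and P(X ≥ 12 | 0.70) = 0.818. These agree with the stated 3.5% and 80%, and that calculation is not in question. No operating characteristics are given for the stopping rules.

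**Step 2: which trigger fires.** Take an irreversible grade 3+ neurological deficit in an expansion subject.

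| Onset and attribution | DLT under 5.3? | Rule 1 | Rule 2 |
|---|---|---|---|
| During infusion, attributed to drug | Yes | No | Counts towards the 20% |
| After infusion, definitely procedure, MRI evidence | Yes, if within 14 days | Fires at one case | No |
| After infusion, procedure but less than definite, or no MRI evidence | Yes, if within 14 days | No | No |
| After infusion, attributed to MTX110/gadoteridol | Yes, if within 14 days | No | No |

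The last two rows are the gap, and no number of such cases closes it.

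The last row takes 'procedure' as separate from the drug. Section 7 separates catheter placement from use of the drug, and 5.3 names procedure and drug as alternatives. However, the attribution scale in 7.1 combines study treatment and surgery in one rating, so the attribution that rule 1 needs cannot be read from the recorded scale. If 'procedure' did include the infused drug, a definite, MRI-supported drug effect would fire rule 1, but less certain ones still would not.

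**Step 3: how often rule 2 fires.** Assume a denominator of 19 and a single look at the end; the plan states neither.

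- 3/19 = 15.8% and 4/19 = 21.1%, so more than 20% means at least 4 children.
- P(X ≥ 4) = 1 − Σ(x = 0 to 3) C(19, x) pˣ (1 − p)^(19 − x).
- At p = 0.15: 1 − (0.0456 + 0.1529 + 0.2428 + 0.2428) = 0.316.
- At p = 0.10, 0.20 and 0.25: 0.115, 0.545 and 0.737.

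Here p is the rate of irreversible deterioration *during infusion*. If the total rate is 20% but half begins later, then p = 0.10 and the probability falls from 0.545 to 0.115. If all of it begins later, rule 2 cannot fire.

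**Step 4: sensitivity to what is unstated.** At p = 0.15:

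- Denominator 26 (the minimum enrolment in section 3.2), one look: 5/26 = 19.2% and 6/26 = 23.1%, so 6 are needed and P(X ≥ 6) = 0.185.
- Denominator growing to 19, checked after every subject from the fifth: probability of ever exceeding 20% = 0.503.

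The same sentence therefore fires with probability between about 0.19 and 0.50 across these three readings.

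**The case against.** A reader might infer that drug-related or late harm never triggers any review. The documents do not support that, for three reasons.

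- **Rule 1 has no time window.** One late, MRI-supported deficit definitely related to the procedure stops the study.
- **Rule 2 has no attribution condition.** Drug harm during infusion counts, and section 5.1 estimates infusions of up to 12.5 hours a day with one catheter.
- **Routine review continues in every phase.** An irreversible grade 3+ deficit would ordinarily be a serious adverse event (7.1.3). Such events are reported within one business day whatever their cause (7.4) and reviewed by the DSMC on an ongoing basis and at six-weekly meetings (7.2). If suspected and unexpected, they go to FDA within 15 days, or 7 if fatal or life-threatening (7.4.4). Appendix E also provides for enrolment to be halted on safety grounds.

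The Appendix E rate alert should not be dismissed either. The Investigator Brochure is not among the documents. If its rates are as low as Table 13, which shows one grade 1 fatigue, a single grade 3 event might exceed them.

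Finally, requiring definite attribution and MRI evidence has a purpose: it helps to separate treatment harm from tumour progression in a disease with a median survival of about 9 months.

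All of this stands and limits the point. It does not remove it: none of these routes has a numeric threshold or forces a halt, whereas 10.3 exists to force one.

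**Conclusion.** The concern holds in a limited form. What is missing is a prespecified mandatory stop in the expansion for irreversible grade 3+ neurological harm that starts after the infusion and is attributed to MTX110/gadoteridol, is less than definitely procedure-related, or lacks MRI evidence. For that class 10.3 forces no stop at any frequency, although 5.3 already counts such harm as a DLT when it falls within 14 days. This rests on reading the text, including 'procedure' as distinct from the drug, and not on a calculation.

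The rule 2 probabilities (0.316 at 15%, 0.545 at 20%) are illustrations. They assume a denominator of 19, a single final look and hypothetical event rates. Their spread under other readings shows that the rule is under-specified; it does not show that 20% is the wrong threshold.

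**What to change.** In section 10.3:

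- Reconcile the scope of the neurological review trigger with 5.3: attribution to the procedure or to MTX110/gadoteridol, and the 14-day post-infusion window. Section 5.3 counts the 14 days from the start of the procedure in one sentence and after the infusion in another, so say which is meant.
- State that the trigger applies in the expansion and in every cycle.
- For both 20% rules, name the denominator and the look times.
- Make the attribution that the trigger needs recordable, since the scale in 7.1 does not separate procedure from drug.

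Do not simply delete the infusion-time limit from rule 2. Without a window and an attribution condition, tumour progression would trip it.

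The change takes a few sentences. The price is possible additional pauses for DSMC review, including for events later judged to be progression. The trigger calls for a study-level review and does not dictate the care of any child.

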10.4 Stratification Factors

There are no stratification factors.

10.5 Analysis of Endpoints

Intent-to-Treat Population (ITT): The ITT population will include all subjects who are enrolled in the study. The ITT population will be the primary population for evaluating efficacy and subject characteristics.

As-Treated Population (AT): The AT population will include all subjects who receive at least 1 dose of study drug. The AT population will be the primary population for evaluating safety.

Analysis of Primary Endpoint

- Safety of repeated CED of MTX110 following standard of care focal radiotherapy will be assessed by monitoring for adverse events, scheduled laboratory assessments, vital sign measurements, and physical examinations for subjects who receive the drug. The severity of toxicities will be graded according to the NCI CTCAE v4.0. Adverse events and clinically significant laboratory abnormalities (meeting Grade 3, 4, or 5 criteria according to CTCAE) will be summarized by maximum intensity and relationship to study drug(s). Grade 1 and 2 adverse events will be summarized if related to study therapy. Descriptive statistics will be utilized to display the data on toxicity.

Analysis of Secondary Endpoint

- We will assess the preliminary efficacy using overall survival at 12 months (OS12) in 19 evaluable DIPG patients treated within the expansion cohort which will include subjects treated as part of the dose escalation portion of the trial on the recommended phase 2 dose (RP2D). Analyses will be performed after all enrolled subjects have completed 12 months, or whenever the status of all subjects has been established, whichever comes first. The primary analysis will be based on the Kaplan-Meier method. Kaplan-Meier estimates and the associated 95% CIs will be calculated for OS12. As described above, if 12 or more of the 19 patients are alive at 12 months, the null hypothesis that OS12 is 40% will be rejected.

Analysis of Exploratory endpoint

The exploratory aims associated with this study will be descriptive and will be limited to frequency tables and summary statistics.

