Exploratory Objectives	
 • To assess the magnetic resonance image-guided intracranial injection procedure in patients with DIPG by correlating the observed distribution of gadoteridol to pre-treatment modeling of the drug distribution utilizing predictive imaging software. • To assess Quality of Life (QOL) in pediatric patients with newly diagnosed DIPG treated with MTX110 co-infused with gadoteridol given by intratumoral CED. • To perform central review of imaging to explore MR qualitative and quantitative measures as markers of disease response and/or progression and treatment effect in comparison to institutional evaluation of disease response and/or progression.

Study Design	This is an open-label, ascending dose, single arm phase I/II study of MTX110 delivered by CED in patients with DIPG following standard of care focal radiotherapy. We will start with a single dose drug concentration of 30 μ M using a total volume of 3mL and administer MTX110 on day 1 only; we will then first dose escalate by the number of days MTX110 is given: 30 μ M concentration, 3 ml total volume, administration will occur on day 1 and 2. We then will start to dose escalate the total volume that is being administered on days 1 and 2. Once the RP2D total volume has been determined, we will then escalate the concentration of MTX110 that is being administered on days 1 and 2. The accelerated dose escalation design will allow intra-patient dose escalation. The concentration of gadoteridol (ProHance) will be 0.5 mM which is the same concentration that is being used for other PNOc studies; both agents will be combined and co-infused via the same catheters. A maximum of 2 catheters will be placed.
Number of patients	The number of subjects enrolled will depend upon the DLTs observed and the number of dose levels tested as the study progresses in accordance with an accelerated dose escalation design (ATD) followed by a 3+3 design. The ATD is expected to enroll 1 to 7 subjects with a minimum of 5 patients in the 3+3 design. Additional subjects might be needed if dose de-escalations need to occur. After review of the initial dose levels as well as achieved coverage areas of the tumor, the study team will also assess if additional dose levels should be tested to achieve adequate tumor coverage. In the pilot efficacy study we will enroll a total of 19 evaluable subjects.

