Duration of Therapy	Eligible subjects will receive MTX110 after completion of standard focal radiotherapy (minimum of 28 days, maximum of 14 weeks from radiation therapy). Treatment will occur every 4-8 weeks. Treatment will continue for up to 24 months or until tumor progression or intolerable toxicity. If subjects continue to derive clinical benefit, discussion with investigators and study sponsor will determine feasibility and clinical appropriateness to continue therapy beyond 24 months.
Duration of Follow up	All subjects will be followed for safety, time to tumor progression and overall survival.
Duration of study	The study will reach completion approximately 3 years from the time the study opens to accrual.
Study Drugs	MTX110 is a water soluble formulation of panobinostat, administered via CED; concentration of gadoteridol (ProHance) will be 0.5 mM in all dose levels; both agents will be combined and co-infused via the same catheters.

Safety Assessments
	
We will use CTCAE version 4.0 for adverse event reporting; surgical complications will be graded as outlined in the protocol. Subjects will undergo clinical evaluation and brain MR imaging prior to any CED to assess for related toxicity, as well as tumor status. Toxicity is defined per standard pediatric phase I guidelines including interruption of planned therapy > 10 weeks to allow for recovery from toxicity of prior CED MTX110 injection.

Efficacy Assessments
	
We will assess the preliminary efficacy using overall survival at 12 months (OS12) in 19 evaluable DIPG patients treated within the expansion cohort which will include subjects treated as part of the dose escalation portion of the trial on the recommended phase 2 dose (RP2D). The most recent Children’s Oncology Group study that treated children newly diagnosed with DIPG with a combination of radiation therapy and temozolomide resulted in an OS12 rate of 40% (SD ± 6.5%). A sample size of 19 patients achieves 80% power to detect a difference of 30% using a one sided exact binominal test. The target significance level is 5% and the actual significance level is 3.5% with this test. If 12 or more patients are alive at 12 months, the null hypothesis that OS12 is 40% will be rejected.

Unique Aspects of this Study
	
This is the first study to evaluate the safety and preliminary efficacy of the use of repeated CED of MTX110 with real time gadoteridol imaging in children with DIPG.

EXPERIMENTAL DESIGN SCHEMA

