Newly Diagnosed Diffuse Intrinsic Pontine Glioma

Phase I Study

Open to patients 2 years to less than or equal to 21 years of age with newly diagnosed DIPG who have completed focal radiotherapy (to begin treatment ≥ 28 days to ≤ 14 weeks from completion of radiation therapy). Enrollment occurs after completion of radiation therapy.

We will assess an anticipated 7 dose levels using an accelerated, intra-patient dose escalation scheme:

- **Dose level 1:** Single CED of 30 μ M MTX110 on 1 day (day 1); Total volume 3 mL
- **Dose level 2:** Repeated CED of 30 μ M MTX110 on 2 consecutive days (days 1, 2); Total volume 6 mL (3 mL on each day)
- **Dose level 3:** Repeated CED of 30 μ M MTX110 on 2 consecutive days (days 1, 2); Total volume 8 mL (4 mL day on each day)
- **Dose level 4:** Repeated CED of 30 μ M MTX110 on 2 consecutive days (days 1, 2); Total volume 10 mL (5 mL day on each day)
- **Dose level 5:** Repeated CED of 30 μ M MTX110 on 2 consecutive days (days 1, 2); Total volume 12 mL (6 mL day on each day)
- **Dose level 6:** Repeated CED of 60 μ M MTX110 on 2 consecutive days (days 1, 2); Total volume 12 mL (6 mL day on each day)
- **Dose level 7:** Repeated CED of 90 μ M MTX110 on 2 consecutive days (days 1, 2); Total volume 12 mL (6 mL day on each day)

Once these dose levels have been assessed, a detailed review of the safety and efficacy data will be performed and the study team will discuss with the FDA and the DSMC to determine either further dose escalation or enrollment into the phase II study.

**Of note, timing of follow-up day 2 infusion will be determined pending patient's return to pre-infusion baseline neurological exam or equal or less than grade 1 toxicities, but will occur no later than 48 hours after completion of infusion on day 1; if patient's neurological exam has not returned to pre-infusion baseline by 48 hours from completion of day 1 infusion, day 2 CED procedure will be canceled.

Phase II Study (Expansion Cohort)

A total of 19 subjects will be enrolled to assess the clinical efficacy of the RP2D within the confines of this pilot study.

LIST OF ABBREVIATIONS

AA	Anaplastic astrocytoma
AE	adverse event
ALP	alkaline phosphatase
ALT	alanine aminotransferase
ANC	absolute neutrophil count
AST	aspartate aminotransferase
ATD	Accelerated titration design
AUC	area under the curve
BUN	blood urea nitrogen
CBC	complete blood cell (count)
CED	Convection-Enhanced Delivery
CNS	Central Nervous System
CR	complete response

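### Section 10.5 makes all enrolled subjects the primary efficacy population but assesses OS12 in 19 evaluable RP2D subjects, leaving the Kaplan-Meier set and membership of the 19 open

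*Combined protocol and SAP*

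**What the plan says.** Section 10.5 defines the population first: "The ITT population will include all subjects who are enrolled in the study". It then gives that population its role: "The ITT population will be the primary population for evaluating efficacy and subject characteristics". Section 3.2 puts total enrolment at 26 or more, across every dose level tested.

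For the secondary endpoint, Section 10.5 then names a different set: "in 19 evaluable DIPG patients treated within the expansion cohort which will include subjects treated as part of the dose escalation portion". The escalation-phase subjects meant are those given the RP2D. The same paragraph:
- times the analysis by the whole study: "Analyses will be performed after all enrolled subjects have completed 12 months", or earlier once every subject's status is known;
- makes Kaplan-Meier the primary analysis, without saying in which subjects;
- rejects an OS12 of 40% if at least 12 of the 19 are alive at 12 months.

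Other parts of the protocol describe the 19 differently. Abstract, Number of patients: "In the pilot efficacy study we will enroll a total of 19 evaluable subjects". Abstract, Efficacy Assessments: "19 evaluable DIPG patients treated within the expansion cohort which will include subjects treated as part of the dose escalation portion of the trial". Experimental Design Schema, Phase II: "A total of 19 subjects will be enrolled to assess the clinical efficacy of the RP2D within the confines of this pilot study". The first and last read as a cohort to be enrolled. The second, like Section 10.5, includes some escalation-phase subjects.

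Section 9.1.1 defines evaluability for toxicity, objective response and non-target response, but not for survival. On dose, the Abstract says: "The accelerated dose escalation design will allow intra-patient dose escalation". Sections 5.5 and 10.2 repeat this. Section 9.1.5 times OS from diagnosis.

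**The concern.** Section 10.1 lists OS12 as the only secondary efficacy endpoint. PFS is defined in Section 9.1.4 but has no planned analysis. The ITT sentence therefore cannot be set aside as governing some other efficacy analysis. It and the OS12 paragraph name different sets for the same endpoint.

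Two things are at stake. First, an analyst who takes the ITT rule at its word would pool children treated below the RP2D into the Kaplan-Meier OS12 estimate. Another would restrict it to the 19. Both would be following Section 10.5.

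Second, the 19 are not pinned down. Suppose a child who began at a lower level and was later escalated to the RP2D counts. That child enters the set only by surviving to the cycle at which the RP2D was given, yet the survival clock starts at diagnosis. The time in between is immortal time, and it favours rejection of the 40% null. In a small open-label trial, such membership questions should be settled before outcomes are known.

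**Working it through.** **1. The plan's own figure.** Inputs from Section 10.3: n = 19, null OS12 40%, alternative 70% (a difference of 30 points), one-sided exact binomial test, reject at 12 or more.
- Level: P(X ≥ 12), X ~ Bin(19, 0.40) = 0.0352. The plan states 3.5%.
- Power: P(X ≥ 12), X ~ Bin(19, 0.70) = 0.818. The plan states 80%.

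The design arithmetic is correct.

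**2. Effect of the population on the Kaplan-Meier estimate.** Section 3.2 gives at least 26 enrolled. I assume 19 at the RP2D and 7 below it, with true OS12 of 70% and 40% respectively. Neither the split nor the lower-dose rate is in the documents.
- Expected OS12 in the 19: 70%.
- Expected OS12 in all enrolled: (19 × 0.70 + 7 × 0.40)/26 = (13.3 + 2.8)/26 = 61.9%.

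The choice of set moves the expected estimate by about 8 points.

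**3. Effect of counting escalated children on the level of the test.** The number of such children is not given. Assumptions:
- first CED at month 3 from diagnosis;
- 40% OS12 among subjects alive at that point, with exponential survival, so survival from month 3 to month t is S(t) = 0.4^((t − 3)/9);
- the RP2D is level 7, and a child rises one level per cycle;
- cycles last 4 weeks (0.92 month) or 8 weeks (1.84 months), the interval in Section 5.5;
- the children counted are those who started nearest the RP2D: level 6, then 5, then 4.

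A child starting j levels below the RP2D reaches it at t = 3 + j × cycle length. Having survived to t, the child is alive at month 12 with probability q = 0.4/S(t).

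| Levels below RP2D at start | q, 4-week cycles | q, 8-week cycles |
|---|---|---|
| 1 | 0.439 | 0.482 |
| 2 | 0.482 | 0.582 |
| 3 | 0.530 | 0.702 |

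With k such children, the level is P(B + A₁ + … + A_k ≥ 12), where B ~ Bin(19 − k, 0.4) and A_j is 1 with probability q_j.

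For k = 1 this is P(Bin(18, 0.4) ≥ 12) + q × P(Bin(18, 0.4) = 11) = 0.0203 + q × 0.0373. Setting q = 0.4 returns 0.0352. With q = 0.439 it is 0.0367, and with q = 0.482 it is 0.0383.

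| Escalated children counted | Level, 4-week cycles | Level, 8-week cycles |
|---|---|---|
| 0 | 3.5% | 3.5% |
| 1 | 3.7% | 3.8% |
| 2 | 4.0% | 4.6% |
| 3 | 4.5% | 6.0% |

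Of these cases, only three children with 8-week cycles exceeds the 5% target.

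**The case against.** The strongest defence is that a general default followed by an endpoint-specific set is an ordinary layout, and the specific text governs. Section 10.3 separates a safety study from an efficacy study, so enrolled in the study might mean the efficacy cohort. For the test, this defence succeeds. A reader might infer that the cut-off of 12 could be applied to all enrolled subjects, with a grossly inflated error rate. The documents do not support that, because Section 10.5 ties the count to the 19. For the Kaplan-Meier estimate the defence does not succeed. Section 10.5 defines ITT without restriction to a phase or dose, times the analysis on all enrolled subjects, and names no set for the estimate.

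A second defence is that the Kaplan-Meier estimate and the binomial count cannot disagree. Within the 19, with every 12-month status known, Kaplan-Meier OS12 equals the simple proportion. That is right. The disagreement is between sets, not methods.

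A third is that only the word evaluable is open, since number, cohort, treatment and dose are all stated. A reader might infer that early deaths could be dropped as non-evaluable and replaced. Nothing in the text permits that, and Section 6.3 follows off-treatment subjects until death. The gap is a missing definition, not a rule allowing exclusion. It still has consequences. Section 10.3 anticipates subjects who receive no drug because of surgical complications. Such a child belongs to ITT, but the plan does not say whether the child belongs to the 19.

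Finally, the text can be read as counting only escalation-phase children first assigned to the RP2D. On that reading the immortal-time point falls away. Diagram 2 in Section 10.2, on intra-patient escalation, was not visible in the copy read, so the point rests on the text alone.

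**Conclusion.** The concern holds in a limited form. Section 10.5 gives two different sets for the only secondary efficacy endpoint and does not say which one the Kaplan-Meier OS12 estimate uses. Under the assumed split and rates, that choice is worth about 8 percentage points (61.9% against 70%). The 12-of-19 rule is not in doubt as a calculation.

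Membership of the 19 is undefined in two respects: what evaluable means for survival, and whether children escalated into the RP2D count. The second matters only if they do count. The rise in level is then small for one or two children, staying below 5%, and reaches 4.5%-6.0% with three. Those figures depend on the assumed survival shape, first-CED date, RP2D level and pace of escalation, none of which the documents fix beyond the 4-8 week interval.

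This should be fixed, but its reach is limited. OS12 is a secondary, preliminary endpoint in a trial whose primary endpoint is safety.

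**What to change.** In Section 10.5, define one OS12 analysis set: the first 19 subjects assigned to the RP2D at their first CED cycle, including escalation-phase subjects who started at that level. Count all of them by vital status at 12 months from diagnosis, with no outcome-related replacement. State that this is what evaluable means for OS12, and that both the Kaplan-Meier OS12 estimate and the 12-of-19 rule use this set.

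Report children who reached the RP2D by intra-patient escalation separately, with a sensitivity analysis that adds them. Make the all-enrolled ITT analysis descriptive, by dose level. Align the Abstract (Number of patients; Efficacy Assessments), the Experimental Design Schema and Sections 10.3 and 10.5 on whether escalation-phase subjects fall within the 19.

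The cost is wording in those places. The 19/12 design, its 3.5% level and its 82% power are unchanged. A few escalated children may no longer count toward the 19, so slightly more expansion enrolment may be needed.
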